8.1. Allocation to Treatment

This trial is open label. All subjects will receive Axitinib. The starting dose of Axitinib will be 5 mg orally twice daily. The dose will be escalated to 10 mg orally BID (see below) or modified as needed for toxicities (see below).

8.2. Drug Supplies

This trial will utilize the commercially available, marketed Axitinib. Pfizer, Inc. will provide the medication free of charge.

8.2.1. Formulation and Packaging

Axitinib will be supplied as 1-mg and 5-mg film coated tablets for oral administration (Table 7). The appropriate dose may be achieved by any combination of these tablets during the dose titration phase, and pills will be counted into prescription bottles accordingly. Every effort will be made to simplify dosage (decrease the number of tablets, and limit to a single kind of tablets, either 1-mg or 5-mg) once stable dose is achieved. The tablets may not be split in order to achieve the desired dose. At each visit, patient will be asked how many doses were missed and when. This information will be recorded in the patient study record. Please see "**Patient Follow-up Form**".

8.2.2. Administration

Axitinib will be administered orally at 5 mg twice a day (morning and evening), starting on Day 1 of the study. Tablets can be taken with or without food, at approximately the same time each day. Doses should be taken approximately 12 hours apart. Patients should be instructed that if they vomit any time after taking a dose, that they must not "make it up" with an extra dose, but instead resume subsequent doses as prescribed. On day of visit patient may hold their morning dose until assessed by clinic. Missed doses may be taken late, up to 3 hours before the next scheduled dose, otherwise should be skipped.

The patients will be asked to bring medication bottles to each follow-up visit, and remaining pills in bottle will be counted at each visit to document compliance. This information will be recorded in each patient's data file.

Dose	Dispensed as
10 mg BID	2x5mg tablets BID
7 mg BID	1x5mg tablets + $2x1mg$ tablets BID
5 mg BID	1x5mg tablets BID
3 mg BID	3x1mg tablets BID
2 mg BID	2x1 mg tablets BID
	Dose 10 mg BID 7 mg BID 5 mg BID 3 mg BID 2 mg BID

Table 7.	Available	Axitinib	Dose]	Levels
1 uoic /.	1 i vallable	1 minino	D050 .	

Patients experiencing drug reaction greater than CTCAE Grade 2 should undergo dose modification as recommended in section 8.2.4.

8.2.3. Dose escalations

Dose escalation is planned at 2 weeks (to 7 mg BID) and at 3 weeks (to 10 mg BID), in the absence of toxicities grade 2 or greater since last follow-up. Dose escalation may be resumed after at least 1 week if all toxicities have diminished to grade 1 or less since last follow-up. Each patient will be seen in clinic at 2, 4, 8 weeks after initiation of treatment and at monthly intervals thereafter, unless more frequent follow-up is clinically indicated. Telephone call to the patient must be made by a study staff member (a doctor or a nurse) at 1 and 3 weeks, +/- 3 days. During these calls, toxicity assessment will be conducted, per patient report, and toxicity management advice given. During the Week 3 call, if toxicities are grade 1 or less since last follow-up, Axitinib dose escalation to 10 mg BID will be made. Dose escalation up to 10 mg po BID may be resumed after at least 1 week if all toxicities have diminished to grade 1 or less (see below), and measures have been taken to reasonably prevent recurrence of these toxicities with the higher dose. The contents of each planned and patient-initiated phone called will be recorded in patient's study record.

If a patient has a dose reduction for study drug related toxicity, the dose may be considered for re-escalation in patients who tolerate the lower dose without toxicities above Grade 1 for at least 1 week, and measures have been taken to reasonably prevent recurrence of these toxicities with the higher dose.

8.2.4. Dose Interruption and Reductions

Adverse events and other symptoms will be graded according to the current Common Terminology for Adverse Events version 4.03 (CTCAE v4.03). This section contains management of adverse events except hypertension, hemoptysis and proteinuria which are discussed in subsequent sections.

Patients developing a treatment-related CTCAE Grade 1 or 2 adverse event will have their dose continued at the same dose level. Patients developing a treatment-related CTCAE Grade 3 or above adverse event will have dose reductions as described below.

Treatment delays due to drug-related toxicity > 2 weeks will result in discontinuation of treatment. Patients removed from treatment for intolerable toxicity will still be followed for survival.

The criteria for dose modification for study drug related adverse events is summarized Table 8 below.

Table 8. Criteria for Dose Modification for Axitinib Related Adverse Events other than Hypertension, Hemoptysis, or Proteinuria

Related Adverse Events	Intervention
Grade 1	Continue at same dose level
	May escalate dose per protocol
	Manage toxicities as medically necessary
Grade 2	Continue at same dose level
	Manage toxicities as medically necessary
Grade 3 nonhematologic	Decrease dose to one lower dose level
drug-related toxicity	Manage toxicities as medically necessary
	Treatment may be interrupted up to 2 weeks per investigator discretion
Grade 4 nonhematologic drug-related toxicity or Grade 4 hematologic toxicity*	Interrupt dosing (up to 2 weeks); re-start at one lower dose level as soon as improvement to CTCAE Grade 2. If patient requires dose reduction below 2 mg BID, discontinue trial participation. Manage toxicities as medically necessary
*Patients who develop grade 4 lymphopenia may continue study treatment without interruption.	

Guidelines for dose reductions for specific adverse events are provided in the following sections.

8.2.4.1. Axitinib Dose Reduction for Hypertension

Patients treated with Axitinib will monitored for hypertension closely in the office. Blood pressure will be monitored closely at routine visits. If hypertension is noted at the time of the initial encounter, it will be checked 5 minutes after sitting quietly.

Guidance on dose interruption and reduction for hypertension is summarized in Table 9 below. If "white coat hypertension" is suspected by the clinician same anti-hypertensive regimen and dose of Axitinib can be continued.

Table 9. Hypertension Management Plan for Axitinib

Degree of Blood Pressure Elevation	Management
2 BP readings separated by at least 30 min show systolic pressure 141-160 mm Hg OR diastolic pressure 91-100 mm Hg	If not on maximal antihypertensive treatment, institute new or additional antihypertensive medication and maintain dose of study drug. If on maximal antihypertensive treatment (3 agents including a diuretic, and no further safe and efficacious escalation of antihypertensive therapy is deemed possible by the investigators), reduce study drug to one lower dose level.
2 BP readings separated by at least 30 min show systolic Pressure 161 or above OR diastolic pressure 101 or above	Interrupt dosing; adjust antihypertensive medication; as soon as BP is 140/90 mm Hg or less, restart study drug at one lower dose level.
Recurrent hypertension following previous dose reduction (2 BP readings separated by at least 30 min show systolic pressure 141-160 mm Hg OR diastolic pressure 91- 100 mm Hg	Repeat study drug dose reduction by one lower dose level. If a patient requires dose reduction below 2 mg BID, take off study.
Hypertensive urgency or emergency while on study drug, with any blood pressure level above 140/90	Take patient off study immediately. Manage as medically appropriate, in the appropriate hospital setting.

If study drug is held, patients receiving antihypertensive medications should monitor closely for hypotension. Plasma half-life of Axitinib is 2-4 hours and BP usually decreases within 1-2 days following dose interruption.

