7. STUDY PLAN

7.1. Study overview

The patients will receive 5 mg Axitinib twice a day. Dose escalation is planned at 2 weeks (to 7 mg BID) and at 3 weeks (to 10 mg BID), in the absence of toxicities grade 2 or greater. Dose escalation may be resumed at next visit if all toxicities have diminished to grade 1 or less (see

below) since last follow-up. Each patient will be seen in clinic at 2, 4, 8 weeks after initiation of treatment and at monthly intervals thereafter, unless more frequent follow-up is clinically indicated.

During follow-up visits, we will assess the toxicities, including checking vital signs, review of systems, physical exam and CBCDP, comprehensive metabolic panel, test for proteinuria. TSH should be checked within 14 days of cycle 1, day 1 then should be done every 2 weeks for two assessments. Following completion of these assessments, TSH should be checked following the completion of even numbered cycles of chemotherapy.

Telephone call to the patient must be made by a study staff member (licensed RN or MD) at 1 and 3 weeks. During these calls, toxicity assessment will be conducted, per patient report, and toxicity management advice given, including initiation or titration of anti-hypertensive treatment. During the Week 3 call, if toxicities are grade 1 or less since last follow-up, dose escalation to 10 mg BID will be made. Dose escalation may be resumed at least 1 week later if all toxicities have diminished to grade 1 or less (see below), and measures have been taken to reasonably prevent recurrence of these toxicities with the higher dose since last follow-up.

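### The white-coat exception in section 8.2.4.1 has no blood-pressure ceiling and needs no confirmation, so clinician suspicion alone can set aside Table 9's axitinib hold and dose reductions

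*Combined protocol and SAP*

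**What the plan says.** Section 8.2.4.1 presents Table 9 as guidance on interrupting and reducing axitinib for hypertension. The next sentence is the exception: if white-coat hypertension "is suspected by the clinician same anti-hypertensive regimen and dose of Axitinib can be continued". It names no row of the table, no upper pressure and no confirming measurement.

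Table 9 itself makes no mention of white-coat effect. Its rows are as follows.

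- **141-160 systolic or 91-100 diastolic, two readings at least 30 minutes apart.** "If not on maximal antihypertensive treatment, institute new or additional antihypertensive medication and maintain dose of study drug". If the patient is already on maximal treatment (three agents including a diuretic, with no safe and effective escalation left), axitinib goes down one level.
- **161 systolic or 101 diastolic or above, two readings at least 30 minutes apart.** "Interrupt dosing; adjust antihypertensive medication; as soon as BP is 140/90 mm Hg or less, restart study drug at one lower dose level".
- **Recurrence at 141-160/91-100 after an earlier dose reduction.** Axitinib goes down a further level, and the patient comes off study if that would mean less than 2 mg BID.
- **"Hypertensive urgency or emergency while on study drug, with any blood pressure level above 140/90".** The patient comes off study at once.

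The general dose-modification rules in section 8.2.4 do not extend to this event: "This section contains management of adverse events except hypertension, hemoptysis and proteinuria which are discussed in subsequent sections".

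**The concern.** The level of 161/101 is where the protocol's own table tells the clinician to stop dosing. An exception that rests on suspicion alone, with no ceiling, lets that instruction be set aside at any pressure not judged to be an urgency or emergency. If a drug-induced rise is mistaken for a clinic effect, the patient stays on the dose that caused it.

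The setting makes that mistake plausible. Inclusion criterion 7 in section 5.2 requires two baseline readings at or below 140/90, so a patient who later reads 161/101 twice shows a new rise on study drug. Table 2 lists hypertension in 246 of 515 single-agent patients (47.8%), grade 3 or worse in 92 (17.9%), which is the highest grade 3+ rate in that table. What is at stake is patient safety under a stated dosing rule. The efficacy analysis is not involved.

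**Working it through.** There is no figure in the plan to reproduce. The check sets the exception against each Table 9 situation, then looks for a cap elsewhere, then sizes the dose step.

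**1. The exception against Table 9 (section 8.2.4.1)**

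| Situation | Table 9 action on axitinib | Effect of the exception |
|---|---|---|
| 141-160/91-100, not on maximal antihypertensives | Dose maintained | Axitinib is the same either way; only the antihypertensive step is skipped |
| 141-160/91-100, on maximal antihypertensives | One level lower | Reduction set aside |
| 141-160/91-100, recurrent after an earlier reduction | One further level lower | Reduction set aside |
| 161 or above, or 101 or above | Hold, then restart one level lower | Hold and reduction both set aside |

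Only in the first of these situations does the exception leave the axitinib instruction unchanged. That is where the limit belongs. A ceiling at 161/101 alone would still leave two required reductions open to override.

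**2. Is there a cap elsewhere?**

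- Section 8.2.2 sends reactions above grade 2 to section 8.2.4. That section's general rules exclude hypertension, which leads back to 8.2.4.1.
- The recheck after 5 minutes of quiet sitting is not tied to the exception. Like the 30-minute separation of readings where these are taken in clinic, it cannot separate clinic effect from drug effect.
- The urgency or emergency row is not triggered by two readings of 161/101 alone.
- The week 1 and week 3 calls provide for "toxicity management advice given, including initiation or titration of anti-hypertensive treatment" (section 7.1), but they work from patient report and require no reading.
- Section 11 asks for attention to hypertension. Section 10 stops treatment for unacceptable toxicity. Section 12.13 gives quarterly committee review. None states a pressure limit.

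**3. Size of one dose level (Table 7)**

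Fraction forgone = (current dose - next lower dose) / current dose.

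- 10 to 7 mg BID: 3/10 = 30%
- 7 to 5 mg BID: 2/7 = 28.6%
- 5 to 3 mg BID: 2/5 = 40%
- 3 to 2 mg BID: 1/3 = 33.3%

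**4. How long a mistaken judgement could stand**

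Scheduled clinic visits after the start of treatment are at weeks 2, 4 and 8, then monthly (section 8.2.3). The next scheduled clinic measurement is therefore 2 weeks, 4 weeks or about a month away, unless an extra visit is thought to be clinically indicated.

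**5. What cannot be computed**

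The documents give no rate of suspected or mistaken white-coat effect, so no patient count follows. They also give no length of hold. The text after Table 9 says "BP usually decreases within 1-2 days following dose interruption", which describes a fall in pressure and does not say that pressure reaches the 140/90 needed to restart.

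**The case against.** The strongest reply is that this is deliberate latitude. Table 9 is labelled guidance, the exception is permissive, and a clinician who doubts the white-coat explanation may still hold the drug. Two separated readings and a recheck come first, urgency or emergency ends participation, and section 10 and the safety committee stand behind that. True white-coat cases at 161/101 should be few, since entry required readings at or below 140/90. The 17.9% rate is all-causality, pooled over solid tumours, and not defined at 161/101.

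Much of this stands, and it rules out several stronger readings that a reader might infer.

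- **That the protocol contradicts itself, with no way to tell which instruction prevails.** The sentence follows directly on the reference to Table 9 and reads naturally as an exception to it. The defect is the exception's breadth.
- **That patients will be dosed through severe hypertension.** The text permits unchanged dosing but does not require it.
- **That 17.9% of the planned 37 patients are at risk.** That rate measures something else, and it says nothing about how often white-coat effect would be suspected.
- **That a mistake costs a countable number of extra doses over 1-2 days.** The documents give no time to reach 140/90.

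What the reply does not answer is that none of these safeguards sets a limit or asks for evidence. Latitude for white-coat effect does not require an exception that reaches the stop-dosing row and both dose-reduction cases.

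**Conclusion.** The point holds as a patient-safety matter. Suspicion alone, with no ceiling and no confirmation, permits unchanged axitinib at 161/101 or above against a stated hold. It also permits it at 141-160/91-100 against the reductions required on maximal antihypertensives or after an earlier reduction. For a patient in whom the suspicion is mistaken, the cost is a missed hold of unknown length (at 161/101 or above) and one dose level not reduced, 28.6% to 40% of the dose by Table 7.

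This rests on reading the sentence as an exception to the whole table, which is its plain sense. How many patients would be affected cannot be estimated. The binomial test of 6-month survival, its sample size and its type I error are unaffected. It is a cheap improvement to make and no ground for questioning the trial's validity.

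**What to change.** Replace the white-coat sentence in section 8.2.4.1 with:

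> If white coat hypertension is suspected and the readings fall in the first row of Table 9 (141-160 systolic / 91-100 diastolic) in a patient not on maximal antihypertensive treatment and without a previous dose reduction for hypertension, the same antihypertensive regimen and axitinib dose may be continued, with the reason recorded. In all other rows of Table 9, including 161 systolic or 101 diastolic or above, Table 9 governs, unless an out-of-clinic reading of 140/90 or less taken while the patient was still on the current axitinib dose is documented.

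A patient on maximal treatment at 141-160/91-100 is meant to fall under Table 9 as well. The urgency or emergency row should apply whatever an out-of-clinic reading shows; a short clause can say so.

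The confirming reading must be taken on the current dose. A normal reading after a hold is what a drug-induced rise would also produce, so it should not justify restarting at the same dose.

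**Cost.** One sentence, with no mandatory visit or test. Clinicians lose some latitude. The few true white-coat patients without an out-of-clinic reading may have a hold or drop one level. Section 8.2.3 allows later re-escalation, provided there is no toxicity above grade 1 for at least a week and measures are in place to prevent recurrence. A patient who keeps reading high in clinic may in practice need an out-of-clinic reading to restart. Otherwise the limit in section 8.2.4 could be applied: "Treatment delays due to drug-related toxicity > 2 weeks will result in discontinuation of treatment". That limit covers drug-related delays only, and Table 9 does not say where the restart reading must be taken, so this cost should be rare.

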The response to treatment will be assessed clinically at each visit, as well as by appropriate radiologic imaging, starting at 8 weeks +/- 2 weeks and then at 8-week intervals, +/- 2 weeks. Tumor response to therapy will be interpreted by Choi Criteria with interpretation performed by UMCC Tumor Response and Assessment Core. Patients will be taken off trial for significant side effects, per patient preference, or for noncompliance with treatment plan. Beyond progression, survival will be assessed every 12 weeks. Patients will also be followed for 28 days after cessation of study participation for safety monitoring. Patients with confirmed progressive disease who, in the investigator's opinion, continue to receive benefit from Axitinib treatment and who meet the criteria for treatment may continue to receive treatment as described in Section 8.3. Axitinib should be discontinued if there is further evidence of progression defined as an additional 10% or greater increase in tumor burden volume from time of initial progression (including all target lesions and new measurable lesions).

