8.2.4.3. Axitinib Dose Reduction for Proteinuria

At documentation of >1+ proteinuria by dipstick, patients should have a 24-hour urine collection for total protein. Axitinib dosing may continue while waiting for test results.

If ≤ 2 g proteinuria/24 hours is reported, treatment with Axitinib may continue without dose reduction.

If >2 g proteinuria/24 hours is reported, treatment with Axitinib should be interrupted. A twenty-four hour urine collection for total protein and creatinine clearance should be performed weekly until results show \leq 2 g proteinuria/24 hours, at which time treatment with Axitinib may be restarted at one lower dose level. Patients, once restarted on Axitinib, will have every-2-weeks monitoring for proteinuria by semiquantitative testing (e.g., dipstick) as long as the proteinuria reading is higher than 1+. The 24-hour urine collection to monitor the degree of proteinuria should be repeated every 4 weeks until it has decreased to <500 mg/24 hours. If recurrent >2 g proteinuria/24 hours is reported, treatment with Axitinib should be interrupted again. Twenty-four hour urine collection for total protein and creatinine clearance should be performed every 2 weeks until results show \leq 2 g proteinuria/24 hours, at which time treatment with Axitinib may be restarted at one lower dose level. If a patient requires dose reduction below 2 mg BID, stop trial participation.

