13. STATISTICAL METHODS

13.1. Primary Objectives:

The primary aim of this study is to compare 6-month overall survival after treatment with Axitinib in patients with unresectable, recurrent or metastatic head and neck cancer to historical rates. Based on results in the literature, we assume a 6-month mortality rate of **50%** under current standard care in this patient population (11, 52). We will test whether survival after treatment with Axitinib is improved to 70% at 6-months compared to 50%.

Overall survival will be determined from the date of treatment initiation to date of death from any cause. For the primary endpoint, patients that are alive at 6 months following the initiation of study treatment will be considered successful. All other patients will be considered unsuccessful. Patients will be considered evaluable for the primary endpoint if they receive any dose of Axitinib.

13.2. Sample size justification:

We will enroll 37 additional patients for comparison of overall survival. Based on historical data, 6 month OS in heavily pretreated patients such as those included in this study is 50%. Thirtyseven patients will provide 80% power to detect a meaningful difference in proportion alive at 6months (70% vs 50% historically) with a type I error rate of 5%. For the primary endpoint of overall survival we anticipate no missing data and will test whether the proportion alive at 6 months is greater than the historical rate of 50% with an upper tailed test of binomial proportion.

Based on our prior experience at the University of Michigan, we anticipate accrual of approximately 4 patients every 5 months. With this rate of accrual, we can enroll 40 eligible patients in 50 months. With a minimum follow-up of 6 month for each patient, the study will complete in about 56 months.

13.3. Stopping rules for futility:

As we observed considerable evidence of activity in UMCC 2011.053, we plan no interim analysis for futility with data collected in the expansion cohort B. Formal analysis of efficacy will be performed at trial completion.

13.4. Analysis plan:

- To estimate survival rates.

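### Several removal rules end trial participation, not just axitinib, so on a literal reading some living patients could leave survival follow-up before 6 months and be scored as failures

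*Combined protocol and SAP*

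**What the plan says.** Five operative rules remove the patient from the study or trial, not only from the drug:

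- Section 7.1: "Patients will be taken off trial for significant side effects, per patient preference, or for noncompliance with treatment plan".
- Table 8 (Section 8.2.4), Grade 4 toxicity: "If patient requires dose reduction below 2 mg BID, discontinue trial participation".
- Table 9 (Section 8.2.4.1), recurrent hypertension: "If a patient requires dose reduction below 2 mg BID, take off study".
- Table 9, hypertensive urgency or emergency: the patient is also taken off study.
- Section 8.2.4.3, proteinuria: "If a patient requires dose reduction below 2 mg BID, stop trial participation".

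Other sections point the other way. Section 10 lists toxicity, patient preference and non-compliance as reasons for discontinuing treatment. Section 8.2.4 states: "Patients removed from treatment for intolerable toxicity will still be followed for survival". Section 18 provides survival contacts, by phone if need be, about every three months after treatment.

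For the primary endpoint, Sections 13.1 and 14.1 make every dosed patient evaluable and count those alive at 6 months as successes. They then add: "All other patients will be considered unsuccessful". Both sections expect no missing data on this endpoint.

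**The concern.** A single-arm trial with a binary 6-month survival endpoint depends on knowing vital status at 6 months for everyone dosed. If stopping the drug also ends participation, a patient who stops early and is still alive may have no recorded status at that time. No separate rule covers unknown status, so such a patient would fall among those counted as unsuccessful. The error runs one way: 6-month survival is understated and power is lost. Each living patient scored this way lowers the estimate by 1/37, or 2.7 percentage points.

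**Working it through.** **1. Do the follow-up provisions reach each removal rule?**

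| Removal rule | Does a survival follow-up provision clearly cover it? |
|---|---|
| Table 8, Grade 4 toxicity | Most plausibly yes. The 8.2.4 sentence sits in the same section, though the two statements conflict as worded. |
| Table 9, two hypertension rows | Not clearly. 8.2.4 introduces itself as leaving hypertension, hemoptysis and proteinuria to later sections. |
| 8.2.4.3, proteinuria | Not clearly, for the same reason. |
| 7.1, significant side effects | Probably, if these amount to intolerable toxicity under 8.2.4. |
| 7.1, preference or non-compliance | Not by 8.2.4, which covers toxicity only. |

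Section 18 could cover all of them, but it does not say that follow-up after treatment includes a patient already taken off study. Section 7.1 ties its 12-weekly survival checks to the period after progression. For the period after participation ends, it mentions 28 days of safety monitoring.

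**2. The plan's own power figure**

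Inputs from Sections 13.1 and 13.2: n = 37, null 50%, target 70%, type I error 5%, upper-tailed binomial test. The stated result is "Thirtyseven patients will provide 80% power to detect a meaningful difference in proportion alive at 6months".

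Formula: P(X ≥ r | n, p) = Σ from x = r to n of C(n, x) pˣ (1 − p)ⁿ⁻ˣ

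- P(X ≥ 23 | 37, 0.5) = 0.0939
- P(X ≥ 24 | 37, 0.5) = 0.0494, so 24 successes are needed
- Power = P(X ≥ 24 | 37, 0.7) = 0.807

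The stated 80% is reproduced.

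**3. Illustration: k patients forced to failure**

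The 24 successes must then come from the other 37 − k patients, each with a 70% chance of being alive.

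- k = 1: P(X ≥ 24 | 36, 0.7) = 0.737
- k = 2: P(X ≥ 24 | 35, 0.7) = 0.652

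**4. Range for an assumed loss fraction**

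The documents give no rate. Let f be the share of 6-month survivors whose status is never obtained. The success probability becomes 0.70 × (1 − f) under the target and 0.50 × (1 − f) under the null.

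| f (assumed) | Success probability under target | Power | Actual type I error |
|---|---|---|---|
| 0% | 0.700 | 0.807 | 0.049 |
| 5% | 0.665 | 0.656 | 0.025 |
| 10% | 0.630 | 0.480 | 0.012 |

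Under the target, about 37 × 0.70 = 25.9 patients survive to 6 months. The last two rows therefore correspond to about 1.3 and 2.6 patients.

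**5. With follow-up complete**

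No status is unknown, and the planned properties stand: at least 24 of 37, type I error 0.049, power 0.807.

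**The case against.** The best defence is that off study here simply means off treatment. Section 10 lists the same reasons as Section 7.1 under a heading about treatment. Table 6 and the schema both carry survival monitoring. The 28-day safety monitoring in Section 7.1 is worded as an addition to survival assessment, and Section 14.2 counts its own 28-day window from stopping the drug. This reading is coherent and may be what was intended, so the consequence is conditional.

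It does not settle the matter. The protocol uses treatment-only wording nearby, in 8.2.4 for long toxicity delays and in 8.2.4.2 for hemoptysis, so a reader may fairly take the other wording to mean something else. The gaps for hypertension, proteinuria, preference and non-compliance remain.

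The exposure may also be small. From the 5 mg starting dose, Table 7 gives two lower levels (3 and 2 mg), so the below-2-mg rules apply only at a third reduction. Section 1.2 describes good tolerability in the predecessor trial. However, the hypertensive-emergency row and the Section 7.1 rule need no such sequence.

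A reader might infer more than the documents support:

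- **That these patients would have no further contact, or only 28 days of it.** No section bars survival calls, and vital status may be learned by other routes.
- **That the predecessor shows the scale of loss, with 42 enrolled and 30 available for efficacy.** Section 1.2 does not say why the other 12 were unavailable, so this is not a loss-to-follow-up rate.
- **That the step from 24 successes (p = 0.049) to 23 (p = 0.094) measures this defect.** Any 37-patient binomial test has such a boundary.
- **That every early stopper becomes a failure.** Schema footnote 2 would instead call some patients who stop within the first month non-evaluable and replace them, contrary to the any-dose rule in 13.1.

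**Conclusion.** The inconsistency is real and lies in current operative text. Read literally, the removal rules could take some living patients out of survival follow-up before 6 months. Unless their status is obtained another way, they would be scored as unsuccessful and 6-month survival would be biased downward, toward a false negative. For some early stoppers, footnote 2 may lead to replacement instead.

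How many patients this would affect is unknown, and it may be few. The fall in power from 0.807 to 0.737 or 0.652 is an illustration for one or two patients, not a forecast, and the 5% and 10% loss fractions are assumptions. The planned sample size and power are correct as stated. The point merits correction because a small wording change protects the primary endpoint.

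**What to change.** Reconcile Sections 7.1, 8.2.4 (Table 8), 8.2.4.1 (both Table 9 rows) and 8.2.4.3 with Sections 8.2.4, 10 and 18:

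- Stopping axitinib for any reason ends study treatment only.
- Survival follow-up under Section 18 continues through at least 6 months from treatment start.
- Off study is reserved for death, withdrawal of consent to follow-up, or loss to follow-up.
- Schema footnote 2 is brought into line with the evaluable set in Sections 13.1 and 14.1, so that early stoppers are handled in one way.

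The cost is a wording amendment in four sections and the schema footnote. Section 18 already specifies the survival contacts and allows them by phone. The sample size, the test and the thresholds for reducing or stopping the drug are not changed.
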